# Table 10-2. Protocol-required Laboratory Assessments Part C and Part D

#### Hematology: **Serum Chemistry: Coagulation Screening Labs:** (only for patients with a history of Hematocrit (Hct) Albumin (ALB) thrombosis): Hemoglobin (Hgb) Alkaline phosphatase Antithrombin III (ATIII) (ALK-P) Mean corpuscular deficiency hemoglobin (MCH) Alanine aminotransferase Factor V Leiden (ALT; SGPT) Mean corpuscular hemoglobin concentration Aspartate aminotransferase Protein S deficiency (MCHC) (AST; SGOT) Protein C deficiency Mean corpuscular volume Blood urea nitrogen (BUN) Serology: (MCV) Calcium (Ca) HBsAg, HCV, and HIV Platelet count Chloride (Cl) Coagulation: Red blood cell (RBC) count Creatinine Activated partial White blood cell (WBC) thromboplastin time (PTT) Gamma-glutamyl count with differential transferase (GGT) Prothrombin time (PT) **Urinalysis (dipstick):** Glucose **Immunoglobulins:** Glucose Lactate dehydrogenase Total IgG Hemoglobin (LDH) IgG Subclasses: IgG1, Leukocytes Inorganic phosphate IgG2, IgG3, IgG4 Protein Potassium (K) Platelet autoantibodies Sodium (Na) Total bilirubin Direct bilirubin Total protein

Serum and urine human chorionic gonadotropin (hCG) (only for females who are not diagnosed as postmenopausal)

HBsAg = hepatitis B surface antigen; HCV = hepatitis C virus; HIV = human immunodeficiency virus; IgG = immunoglobulin G

Compound: M254 Protocol: MOM-M254-001

Protocol Date and Version:8 Global 28 April 2020

# 10.3 Appendix 3: Adverse Events: Definitions and Procedures for Recording, Evaluating, Follow-up, and Reporting

#### 10.3.1 Definition of AE

#### AE Definition

- An adverse event (AE) is any untoward medical occurrence in a patient or clinical study
  participant, temporally associated with the use of study intervention, whether or not considered
  related to the study intervention.
- NOTE: An AE can therefore be any unfavorable and unintended sign (including an abnormal laboratory finding), symptom, or disease (new or exacerbated) temporally associated with the use of study intervention.

## Events Meeting the AE Definition

- Any abnormal laboratory test results (hematology, clinical chemistry, or urinalysis) or other safety assessments (eg, electrocardiogram [ECG], radiological scans, vital signs measurements), including those that worsen from baseline, considered clinically significant in the medical and scientific judgment of the Investigator (ie, not related to progression of underlying disease).
- Exacerbation of a chronic or intermittent pre-existing condition including either an increase in frequency and/or intensity of the condition.
- New conditions detected or diagnosed after study intervention administration even though it
  may have been present before the start of the study.
- Signs, symptoms, or the clinical sequelae of a suspected drug-drug interaction.
- Signs, symptoms, or the clinical sequelae of a suspected overdose of either study intervention or a concomitant medication. Such overdoses should be reported regardless of sequelae.
- The signs, symptoms, and/or clinical sequelae resulting from lack of efficacy will be reported as
  AE or serious adverse event (SAE) if they fulfill the definition of an AE or SAE. Also, "lack of
  efficacy" or "failure of expected pharmacological action" also constitutes an AE or SAE.

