#### 2.3 Benefit/Risk Assessment

engineered from commercially available IVIg. This increase in sialyation was demonstrated to increase anti-autoimmune and anti-inflammatory activity in preclinical pharmacological experiments. M254 has been evaluated in preclinical pharmacology and nonclinical toxicology studies. Intravenous immunoglobulin is considered standard of care in multiple disease settings notably in ITP. This study has been designed to start with Part A (Netherlands only) where ascending single doses of M254 will be evaluated for safety and tolerability in healthy individuals with all doses of M254 lower than doses considered safe in nonclinical toxicological studies. In Part B, patients with ITP will be administered a dose of M254, which has expected minimum biological activity, escalating up to clinical efficacious doses of increasing platelet counts. Part C will evaluate efficacious

Compound: M254 Protocol: MOM-M254-001

Protocol Date and Version:8 Global 28 April 2020

doses of M254 with crossover to standard of care IVIg. Patients in Part B and C will be assessed for the clinically relevant PD marker of increase in platelet count to identify dose to be evaluated in Part D.

It is expected that M254 will be biologically active at significantly lower doses compared to IVIg, so it is likely to shorten the infusion period without impacting expected efficacy when compared to IVIg in patients with ITP. All participants will be monitored for safety and tolerability as well as for efficacy (in parts with ITP patients) and only those ITP patients who are not at risk of life threatening bleeding with a platelet count  $\geq 15 \times 10^9/L$  will be selected.

Given the dose selection rationale described above, eligibility criteria, and active safety monitoring (including but not limited to platelet count assessment with potential of benefit of receiving same or more efficacious dose level), the study will not introduce unfavorable risk:benefit for the study participants.

For more detailed information on the potential risks and treatment of adverse events (AEs), please refer to the Investigator's Brochure [11].

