### **8.3.6** Clinical Safety Laboratory Assessments

See Appendix 2 for the list of clinical laboratory tests to be performed and to the Schedule of Activities (Section 1.2) for the timing and frequency.

The Investigator must review the laboratory report, document this review, and record any clinically relevant changes occurring during the study in the AE section of the eCRF. The laboratory reports must be filed with the source documents. Clinically significant abnormal laboratory findings are those which are not associated with the underlying disease, unless judged by the Investigator to be more severe than expected for the participant's condition, and will be considered AEs.

All laboratory tests with values considered clinically significantly abnormal during participation in the study should be repeated until the values return to normal or baseline or are no longer considered clinically significant by the Investigator. If such values do not return to normal/baseline within a period of time judged reasonable by the Investigator, the etiology should be identified and the sponsor notified.

Subjects will be in a seated or supine position during blood collection. Instructions for blood collection, processing, storage, and shipping are described in the Laboratory Manual.

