# Events **NOT** Meeting the AE Definition

- Any clinically significant abnormal laboratory findings or other abnormal safety assessments
  which are associated with the underlying disease, unless judged by the Investigator to be more
  severe than expected for the participant's condition.
- The disease/disorder being studied or expected progression, signs, or symptoms of the disease/disorder being studied, unless more severe than expected for the participant's condition.
- Medical or surgical procedure (eg, endoscopy, appendectomy): the condition that leads to the procedure is the AE.
- Situations in which an untoward medical occurrence did not occur (social and/or convenience admission to a hospital).
- Anticipated day-to-day fluctuations of pre-existing disease(s) or condition(s) present or detected at the start of the study that do not worsen.

Compound: M254 Protocol: MOM-M254-001

Protocol Date and Version:8 Global 28 April 2020

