5.1.1 Primary Endpoint

Part A:

 Incidence and severity of adverse events (AEs) following administration of M254 at single dose levels

• Clinically significant changes in clinical safety labs, vital signs, and electrocardiograms (ECGs) with M254 administration

Part B:

- Incidence and severity of AEs following administration of M254 at single dose levels and 1000 mg/kg IVlg
- Clinically significant changes in clinical safety labs, vital signs, and ECGs following M254 administration and 1000 mg/kg IVIg

Part C:

- Incidence and severity of AEs of M254 and 1000 mg/kg IVIg
- Clinically significant changes in clinical safety labs, vital signs, and ECGs following M254 administration and 1000 mg/kg IVIg
- Platelet response after M254 administration compared to IVIg

Part D:

- Incidence and severity of AEs with repeated administration of M254
- Clinically significant changes in clinical safety labs, vital signs, and ECGs with M254 administration

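### The protocol does not settle whether absent platelet response is itself an adverse event, and the SAP's AE tables count whatever is reported

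*Protocol*

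**What the plan says.** **The rule that includes it.** Protocol 10.3.1, under events meeting the AE definition, first makes the signs, symptoms and sequelae of lack of efficacy reportable, on condition that they meet the AE or SAE definition. It then adds, without that condition, that lack of efficacy or "failure of expected pharmacological action" "also constitutes an AE or SAE".

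**The rules that exclude it.** The list of events not meeting the definition names "The disease/disorder being studied or expected progression, signs, or symptoms of the disease/disorder being studied", unless more severe than expected for the participant. It treats abnormal laboratory findings linked to the disease in the same way. Protocol 8.3.6 agrees: "Clinically significant abnormal laboratory findings are those which are not associated with the underlying disease", with the same exception. Protocol 10.3.2 adds that an event which is not an AE cannot be an SAE.

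**Where the count goes.** SAP 5.1.1 lists "Incidence and severity of AEs of M254 and 1000 mg/kg IVIg" among the Part C primary endpoints, with platelet response as a separate primary endpoint. Part B has the corresponding AE endpoint. SAP 18.1.1 tabulates all TEAEs by part and treatment and assigns each to the dosing period in which it falls. It makes no exception for lack-of-efficacy terms. Parts B, C and D are open-label (Protocol 6.3).

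**The concern.** In ITP patients the expected action of both products is a platelet rise, so failure of that action is the efficacy outcome. If it is also an AE, one outcome enters both the efficacy and the safety comparison. The treatment with the weaker platelet effect then shows more AEs, and perhaps more related AEs, with no additional toxicity.

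Because the governing text conflicts, the size of this effect depends on which sentence each investigator follows. Investigators in Parts B to D know which product was infused, so the choice need not be even-handed between treatments.

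**Working it through.** **1. The passages side by side.** Take an ITP patient whose platelet count stays at its baseline level after infusion.
- Under the last sentence of the first list in 10.3.1, this is lack of efficacy and so an AE or SAE.
- Under the second list and 8.3.6, a persistently low count is a finding of the disease under study. It is not an AE unless more severe than expected, and an unchanged count gives no obvious reason to call it that.
- Neither document ranks the two rules or defines lack of efficacy for AE reporting. The platelet criteria in Protocol 8.7 and SAP 17.1.2 define therapeutic counts for the PD parameters and are not linked to AE reporting.

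**2. Which parts are exposed.** Parts B and C set M254 beside IVIg, so a difference in non-response can become a difference in AE incidence. Part D has no IVIg comparator, so only its absolute rate could rise. Part A enrols healthy volunteers and is unaffected.

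**3. Weight of one report.** For a patient with no other AE in the period, one report moves incidence by 1/2 = 50 points in a planned Part B cohort, 1/10 = 10 points in a planned Part C cohort, and 1/20 = 5 points across Part C.

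**4. Direction, from the printed Part C output** (CSR appendix 16.1.9.2, section 4.1, supplied with the SAP; 21 period observations). The printed intervals were reproduced first, as estimate ± t × SE.
- Log ratio of maximum count: −0.7061 ± 2.254 × 0.1172 = −0.970 to −0.442, a ratio of 0.49 (0.38 to 0.64).
- Log ratio of maximum change: −1.2981 ± 2.261 × 0.2049 = −1.761 to −0.835, a ratio of 0.27 (0.17 to 0.43).

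M254 had the weaker platelet effect, so any added events would fall mainly on M254 periods.

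**5. Implied non-response.** Assume normality on the log scale, with SD equal to the square root of the summed variance components: √(0.1077 + 0.06513) = 0.416 for the maximum count and √(0.3740 + 0.1970) = 0.756 for the maximum change. The probability is Φ((ln threshold − LS mean)/SD).
- Maximum below 50: M254 Φ((3.912 − 4.0919)/0.416) = 0.333; IVIg Φ((3.912 − 4.7980)/0.416) = 0.017.
- Change below 20: M254 Φ((2.996 − 3.1437)/0.756) = 0.422; IVIg Φ((2.996 − 4.4418)/0.756) = 0.028.

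The two criteria are taken one at a time. The SAP's definition of a therapeutic count requires both to be met.

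**6. Effect on TEAE incidence.** Let b be the incidence of other AEs, assumed equal on both treatments and independent of response, and let every non-response be reported. Incidence is b + (1 − b) × P(non-response), so the artificial excess on M254 is (1 − b) × (0.3326 − 0.0165) or (1 − b) × (0.4224 − 0.0278).

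| b | Excess, maximum <50 | Excess, change <20 |
|---|---|---|
| 20% | 25 points | 32 points |
| 40% | 19 points | 24 points |
| 60% | 13 points | 16 points |
| 80% | 6 points | 8 points |

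For example, with b = 20% and the first criterion: M254 0.20 + 0.80 × 0.3326 = 46.6%; IVIg 0.20 + 0.80 × 0.0165 = 21.3%; difference 25.3 points. With absent response kept out of the count, the difference is zero by construction.

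**The case against.** The best defence is that the exclusions already deal with the case: non-response in ITP is mostly a count that stays low, which is a finding of the disease. The tables also limit the damage. Events appear by preferred term, so a drug-ineffectiveness term would be a visible row. The list of AEs of special interest in SAP 18.1.1 does not include it. The dose-limiting toxicity definition in Protocol 6.7.2 sets aside clearly unrelated events and gives ITP thrombocytopenia as an example. Relatedness is a clinical judgment. The analysis is descriptive with no hypothesis test (SAP 9.4.3), and SAE recording details are deferred to a Safety Management Plan that is not supplied.

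Most of this stands and narrows the point. It does not remove it, because the inclusive sentence is a stated rule that nothing overrides, and overall and related TEAE totals remain exposed.

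A reader might infer more than the documents support:
- **That a weak response is counted as an AE.** The text speaks of lack of efficacy or failure of expected action, so a partial rise need not qualify. Given the contrary passages, even an absent response only can be counted.
- **That a dose-toxicity pattern would be masked or reversed, worst at the lowest doses.** The preferred-term, special-interest and dose-limiting toxicity rules tell against this. The starting Part B dose is one "which has expected minimum biological activity" (Protocol 2.3), so absence of a rise there is hardly failure of expected action.
- **That Part D is affected in the same way.** It has no IVIg comparison.
- **That the ratio of 0.27 shows high non-response.** It is a ratio of geometric means. The M254 least-squares means back-transform to exp(4.0919) ≈ 60 and exp(3.1437) ≈ 23 × 10⁹/L, so the typical value meets both SAP thresholds.

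**Conclusion.** The concern holds as an unreconciled contradiction in the AE definition that reaches a primary endpoint. Absent platelet response can enter the TEAE counts, inconsistently across sites and with treatment known. Where it does, overall and possibly related TEAE incidence is inflated for the less effective treatment in Parts B and C.

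The tabulated excesses show what is possible. They rest on full reporting of non-response, independence, equal background AE incidence, log-normality, and a small set of estimates obtained after the trial was analysed. Partial reporting would shrink them in proportion if it were equal on both treatments. The supplied documents contain no AE counts, so they do not show that distortion occurred. Severity is moderate: the safety comparison is descriptive, but its numerator should not mix efficacy failure with toxicity.

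**What to change.** **Protocol.** Reconcile the two lists in 10.3.1 with 8.3.6. State that absent platelet response alone is captured by the platelet endpoints and is not itself an AE, while clinical sequelae such as bleeding remain reportable.

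**SAP 18.1.1.** List separately any terms that denote only drug ineffectiveness, and show overall TEAE incidence with and without them. This keeps every reported event in view and can be run on data already collected. It will not catch non-response recorded under another term, such as a low platelet count, so the protocol sentence is needed as well.

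**Cost.** One sentence in the protocol and a small amount of extra programming. No safety information is lost, because sequelae are still reported.

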# Events **NOT** Meeting the AE Definition

- Any clinically significant abnormal laboratory findings or other abnormal safety assessments
  which are associated with the underlying disease, unless judged by the Investigator to be more
  severe than expected for the participant's condition.
- The disease/disorder being studied or expected progression, signs, or symptoms of the disease/disorder being studied, unless more severe than expected for the participant's condition.
- Medical or surgical procedure (eg, endoscopy, appendectomy): the condition that leads to the procedure is the AE.
- Situations in which an untoward medical occurrence did not occur (social and/or convenience admission to a hospital).
- Anticipated day-to-day fluctuations of pre-existing disease(s) or condition(s) present or detected at the start of the study that do not worsen.

Compound: M254 Protocol: MOM-M254-001

Protocol Date and Version:8 Global 28 April 2020

#### 10.3.2 Definition of SAE

If an event is not an AE per definition above, then it cannot be an SAE even if serious conditions are met (eg, hospitalization for signs/symptoms of the disease under study, death due to progression of disease or other criteria being met). For any SAE, refer to the Safety Management Plan for further details of recording and reporting.

#### A SAE is defined as any untoward medical occurrence that, at any dose:

#### a. Results in death

#### b. Immediately life-threatening

The term 'life-threatening' in the definition of 'serious' refers to an event in which the participant was at risk of death at the time of the event. It does not refer to an event, which hypothetically might have caused death, if it were more severe.

#### c. Requires inpatient hospitalization or prolongation of existing hospitalization

In general, hospitalization signifies that the participant has been detained (usually involving at least an overnight stay) at the hospital or emergency ward for observation and/or treatment that would not have been appropriate in the physician's office or outpatient setting. Complications that occur during hospitalization are AEs. If a complication prolongs hospitalization or fulfills any other serious criteria, the event is serious. When in doubt as to whether "hospitalization" occurred, the AE should be considered serious.

Hospitalization for elective treatment of a pre-existing condition that did not worsen from baseline is not considered an AE.

#### d. Results in persistent disability/incapacity

- The term disability means a substantial disruption of a person's ability to conduct normal life functions.
- This definition is not intended to include experiences of relatively minor medical significance such as uncomplicated headache, nausea, vomiting, diarrhea, influenza, and accidental trauma (eg, sprained ankle) which may interfere with or prevent everyday life functions but do not constitute a substantial disruption.

# e. Is a congenital anomaly/birth defect

#### f. Other medically important serious event:

• Medical or scientific judgment should be exercised in deciding whether SAE reporting is appropriate in other situations such as important medical events that may not be immediately life-threatening or result in death or hospitalization but may jeopardize the participant or may require medical or surgical intervention to prevent 1 of the other outcomes listed in the above definition. These events should usually be considered serious.

Examples of such events include invasive or malignant cancers, intensive treatment in an emergency room or at home for allergic bronchospasm, blood dyscrasias or convulsions that do not result in hospitalization, or development of drug dependency or drug abuse.

Compound: M254 Protocol: MOM-M254-001

Protocol Date and Version:8 Global 28 April 2020

# 10.3.3 Recording and Follow-up of AE and/or SAE

#### AE and SAE Recording

- When an AE/SAE occurs, it is the responsibility of the Investigator to review all documentation (eg, hospital progress notes, laboratory reports, and diagnostics reports) related to the event.
- The Investigator will then record all relevant AE/SAE information in the case report form (CRF).
- It is **not** acceptable for the Investigator to send photocopies of the participant's medical records to Sponsor in lieu of completion of the AE/SAE CRF page.
- There may be instances when copies of medical records for certain cases are requested by Sponsor. In this case, all participant identifiers, with the exception of the participant number, will be redacted on the copies of the medical records before submission to Sponsor.
- The Investigator will attempt to establish a diagnosis of the event based on signs, symptoms, and/or other clinical information. Whenever possible, the diagnosis (not the individual signs/symptoms) will be documented as the AE/SAE.
- The Investigator must assign the following AE attributes:
  - Adverse event diagnosis or syndrome(s), if known (if not known, signs or symptoms);
  - Dates of onset and resolution (if resolved);
  - Intensity (or toxicity defined below);
  - Assessment of relatedness to investigational product; and
  - Action taken. Changes in AE severity are to be recorded as a single event worst severity.

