## **6.7.2 Dose Limiting Toxicities**

Dose-limiting toxicities will include any NCI CTCAE v.5 Grade 3 or higher adverse reaction occurring within 4 weeks following the administration of M254.

**Note:** Events considered by the sponsor as clearly unrelated to the study drug will not be considered a DLT, eg, thrombocytopenia related to ITP, accidents, and lab results attributed to other therapies or illnesses.

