#### 8.4.1 Time Period and Frequency for Collecting AE and SAE Information

All SAEs will be collected from the time of consent until the end of study at the time points specified in the Schedule of Activities (Section 1.2).

All AE will be collected from the time of consent until the end of study at the time points specified in the Schedule of Activities (Section 1.2).

Compound: M254 Protocol: MOM-M254-001

Protocol Date and Version:8 Global 28 April 2020

All SAEs will be recorded and reported to the sponsor or designee immediately and under no circumstance should this exceed 24 hours from becoming aware of the event, as indicated in Appendix 3. The Investigator will submit any updated SAE data including but not limited to previously missing information, corrections, or additional details of the event, to the sponsor or designee within 24 hours of the Investigator becoming aware.

Investigators are not obligated to actively seek information about AEs or SAEs occurring after conclusion of the study participation. However, if the Investigator learns of any SAE, including a death, at any time after a participant has been discharged from the study, and he/she considers the event to be reasonably related to the study intervention or study participation, the Investigator must promptly notify the sponsor.

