#### Follow-up of AEs and SAEs

- The Investigator is obligated to perform or arrange for the conduct of supplemental
  measurements and/or evaluations as medically indicated or as requested by Sponsor to elucidate
  the nature and/or causality of the AE or SAE as fully as possible. This may include additional
  laboratory tests or investigations, histopathological examinations, or consultation with other
  health care professionals.
- If a participant dies during participation in the study or during a recognized follow-up period, the Investigator will provide Sponsor with a copy of any postmortem findings including histopathology.
- New or updated information will be recorded in the originally completed CRF.
- The Investigator will submit any updated SAE data to the sponsor within 24 hours of receipt of the information.

Compound: M254 Protocol: MOM-M254-001

Protocol Date and Version:8 Global 28 April 2020

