18.1.1 Adverse Events

All AE summaries will include only treatment-emergent adverse events (TEAE). TEAEs are those starting or increasing in severity on or after the first dose of study drug.

TEAEs occurring following dosing in a specific period but before dosing in the next period will be attributed to that specific period. If the time is missing for an AE on a dosing day then the AE will be attributed to the treatment given on that day.

A TEAE overview table will be included, presenting the number and percentage of subjects reporting TEAEs, subjects reporting TEAEs with outcome=Death, subjects reporting serious TEAEs, subjects who discontinue study drug due to a TEAE, subjects reporting treatment related TEAEs, subjects reporting injection site reactions.

A breakdown of the number of AEs, number and percentage of subjects reporting each AE, categorized by body system and preferred term coded according to the latest version of Medical Dictionary for Regulatory Activities (MedDRA), will be presented by part, treatment and also M254 overall. Subjects will only be counted once within each body system or preferred term. There will be one such table presented for:

- All TEAEs
- TEAEs considered related to study drug
- Serious AEs (SAEs)
- AEs of Special Interest (AESI: systemic and local reactions, hemolysis, infections, flu-like symptoms, rash, myalgia and arthralgia, fever, chills)
- Severe AEs.

A summary of AEs reported, categorized by relationship (categories: related, not related) will also be provided by part, treatment and also M254 overall. AEs reported in the eCRF as 'Possibly', 'Likely' and 'Definitely' will be considered related to study drug, while categories 'None' and 'Unlikely' will be considered not related.

A summary of AEs reported, categorized by severity as recorded on eCRF, will also be provided by part, treatment and also M254 overall.

All AEs recorded on the eCRF will be listed together with MedDRA coding. One listing will contain TEAEs and one listing will contain non-treatment-emergent AEs.

A listing of AEs leading to study drug discontinuation will be provided ('Adverse Event' is reported as primary reason for early termination/study non-completion).

The following missing data will be imputed as defined (for calculations only / will not be presented):

- Missing AE start and / or end times for the calculation of onset and duration will be assumed to be at 00:01 for a start time and 23:59 for end times

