- Missing AE severity or relationship will be assumed to be severe or related, respectively
- Missing AE start times for the determination of treatment emergence will be assumed to occur after treatment unless partial date documents the AE as happening prior to treatment
- Missing AE start times for the determination of treatment assignment will be assumed to occur after treatment on the recorded date one minute after dosing
- Missing AE start date will be assumed to be after treatment for the determination of TEAE and on treatment for single treatment studies but will not be attributed to treatment in studies with multiple treatments

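### AE severity changes are kept on one record at worst grade with no date of worsening, so a worsening after a later dose can be tabulated under the wrong drug or missed as treatment-emergent

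*Protocol*

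**What the plan says.** **Protocol, Appendix 3, section 10.3.3.** The investigator assigns each AE a diagnosis, onset and resolution dates, an intensity, a relatedness assessment and the action taken. On changes in grade the rule is "Changes in AE severity are to be recorded as a single event worst severity". No date of worsening is on the list. Under follow-up, "New or updated information will be recorded in the originally completed CRF", so the original record and its onset date are kept.

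**Protocol 8.4.1.** "All AE will be collected from the time of consent until the end of study". An AE can therefore start before the first dose.

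**SAP 18.1.1.** All AE summaries are restricted to treatment-emergent events, and "TEAEs are those starting or increasing in severity on or after the first dose of study drug". For Parts B and C, "TEAEs occurring following dosing in a specific period but before dosing in the next period will be attributed to that specific period". The imputation rules in the same section work on the start of the event: "Missing AE start times for the determination of treatment assignment will be assumed to occur after treatment". Severity is tabulated by part and treatment from the grade held on the eCRF. Events that are not treatment-emergent appear only in a listing.

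**The concern.** Incidence and severity of AEs is a primary endpoint in every part. In Parts B and C it is a comparison of M254 with 1000 mg/kg IVIg in the same patients (Protocol 3.2 and 3.3; SAP 5.1.1). The single-record rule is serviceable when there is one drug and one dose. Here two drugs are given in turn, and the SAP asks when severity rose. The protocol does not require that information to be collected.

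Two separate problems follow:

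1. **Attribution between drugs.** The grade reached after the second infusion sits on a record whose onset lies in the first period.
2. **Treatment emergence.** The part of the definition that turns on increasing severity needs a date that is not among the required fields.

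The first does not come from the second. The severity clause is tied to the first dose of study drug, not to each period's dose, so it gives no rule for an event that carries over and worsens after crossover.

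**Working it through.** The plan states no figure on this point. The check applies the protocol's recording rule and then the SAP's rules to two timelines. The days and grades are assumed for illustration.

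**Inputs**
- Record content and updating: Protocol 10.3.3.
- Collection from consent: Protocol 8.4.1.
- Treatment emergence, period attribution and severity source: SAP 18.1.1.
- Second infusion: Day 29 at the earliest nominal time, conditional on platelet count (Protocol 4.1.2 and 4.1.3). Those sections do not require ongoing AEs to have resolved first.
- Planned cohort sizes: 2 patients in Part B, 10 in Part C, 20 in Part C overall.

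**Two timelines**

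| | Timeline 1 (Part B or C) | Timeline 2 (any part) |
|---|---|---|
| Start | Day 20 of Period 1, Grade 1 | Day -5, after consent, Grade 1 |
| Dose | Second drug on Day 29 | First dose on Day 1 |
| Worsening | Grade 3 on Day 31 | Grade 3 on Day 2 |
| Record under 10.3.3 | Onset Day 20, Grade 3 | Onset Day -5, Grade 3 |
| Result under SAP 18.1.1 | Grade 3 under the first drug, nothing under the second | Onset before dosing, no dated increase, so not identifiable as treatment-emergent |
| Result if the worsening were dated | Grade 1 under the first drug, Grade 3 under the second | Treatment-emergent, Grade 3 |

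**Direction.** In Part B the sequence is fixed, so Timeline 1 always counts against M254. In Part C it counts against whichever drug came first. In the IVIg-then-M254 sequence, a worsening after M254 is charged to IVIg.

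**Size of one Timeline 1 event.** The shift in severe-AE incidence in each treatment column is 1/n, if all n patients receive both drugs:
- Part B cohort: 1/2 = 50 percentage points.
- Part C cohort: 1/10 = 10 points.
- Part C overall: 1/20 = 5 points.

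The event leaves one column and enters the other, so the M254 minus IVIg difference moves by twice these amounts. In a two-patient cohort it goes from 0 - 50 = -50 points to 50 - 0 = +50 points, a shift of 100. The corresponding shifts are 2 × 10 = 20 points in a Part C cohort and 2 × 5 = 10 points over Part C.

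The documents give no count of AEs that span the second infusion, so an expected bias cannot be calculated.

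**The case against.** Several points on the other side have force.

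- **The eCRF is not among the documents.** The SAP is meant to be read with it. If it holds a dated severity log, the treatment-emergence rule can be applied after all. This stands as a condition on the finding, but 10.3.3 does not ask for such a log.
- **Exacerbations.** Protocol 10.3.1 counts worsening of a chronic or intermittent pre-existing condition as an AE in its own right. A reader might infer that every event starting before dosing and worsening afterwards is lost, or that the severity clause can never be applied. That is too strong. What remains is the acute event that begins between consent and first dose.
- **Infusion reactions.** Protocol 8.3.5 has the signs and symptoms of infusion reactions recorded as individual AEs. A rash or headache that flares after the second infusion and is judged a reaction may get its own record and onset. This narrows the problem but does not cover worsening not judged a reaction.
- **Low frequency and descriptive use.** Doses are normally at least 28 days apart, no formal testing is planned, and events are listed individually. All true. The tables are still the stated summary of a primary endpoint.

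A reader might also infer that Timeline 1 creates a false dose-limiting toxicity and so distorts escalation. The documents do not support this. The DLT definition in Protocol 6.7.2 covers reactions "occurring within 4 weeks following the administration of M254". With dosing on Day 1, the Grade 3 in Timeline 1 is reached 31 - 1 = 30 days later, beyond 28 days, and nothing says the review committee would backdate it to the Grade 1 onset. Escalation review rests on data to about Day 10 (Protocol 4.1.2 and 6.6), before any IVIg is given. SAP 7.2 places escalation reports outside the SAP, Part B is open-label, and events the sponsor considers clearly unrelated are excluded. What stands is an ambiguity: 6.7.2 and 10.3.3 do not together say which date of a worsening event the 4-week window refers to.

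**Conclusion.** The concern holds in a limited form. Followed as written, the recording rule and SAP 18.1.1 place a worsening after the second infusion under the first drug. They also leave an acute event that starts between consent and first dose, and then worsens, unidentifiable as treatment-emergent.

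This rests on three readings. First, the original onset is kept; 10.3.3 does not say so in one sentence, but it follows from the single onset date and updating of the original form. Second, period attribution works on the start of the event, as the imputation rules indicate. Third, the eCRF adds no dated severity change.

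The effect per event is large in cohorts of 2 and 10. The number of such events cannot be derived and is probably low. The point bears on the accuracy of the safety tables, not on dose escalation. It should be corrected because the remedy is cheap and a stated SAP definition depends on it.

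**What to change.** **Protocol 10.3.3 and eCRF guidance.** When an AE ongoing at a dose increases in grade after that dose, record either a dated grade change or a new linked record, with its own causality assessment. Keep the worst-grade rule within a dosing interval.

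**SAP 18.1.1.** Attribute the worsening to the period in which it began, using each period's dose as the reference rather than only the first dose of the study.

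**Data already collected.** The existing onset and resolution dates are enough to list AEs that span a dose. That list bounds how many records could be affected and shows where the source documents need checking.

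**Protocol 6.7.2 and 10.3.3.** The sponsor should reconcile these sections on which date the 4-week window refers to. The choice is the sponsor's.

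**Cost.** One paragraph in Appendix 3, eCRF completion guidance and one sentence in the SAP. There will be a few more AE records, so total event counts rise slightly. The second-period patient count for a term also rises wherever a worsening occurred, which is the intended correction but should be stated in the table footnotes.
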